# Statistical Analysis Plan

Taisho Pharmaceutical R&D Inc.  
Protocol TS121-US201

Final 2.0  
18 Dec 2018

Statistical Analysis Plan (SAP)

CONFIDENTIAL

## Table 4 Listings to be Included in Section 16 of the Clinical Study Report

*Note: Listings that support top line tables or figures are indicated \**

### Study Information

Listing 16.1.7 Randomization and Interactive Response Technology (IRT) Record

### Documentation Of Statistical Methods

Appendix 16.1.9.2.1 Statistical Analysis Details of Table 14.2.2.3 and Table 14.2.2.4 Analysis of Montgomery-Asberg Depression Rating Scale (MADRS) Total Score Change from Baseline

Appendix 16.1.9.2.2 Statistical Analysis Details of Table 14.2.2.5 Analysis of Montgomery-Asberg Depression Rating Scale (MADRS) Total Score Change from Baseline at Week 6/EOT

Appendix 16.1.9.2.3 Statistical Analysis Details of Table 14.2.2.6 Montgomery-Asberg Depression Rating Scale (MADRS) Responders Comparison of TS-121 Treatment versus Placebo at Visit 6 (Intent to Treat Population)

Appendix 16.1.9.2.4 Statistical Analysis Details of Table 14.2.3.2 Summary and Analysis of Clinical Global Impression Improvement (CGI-I) Score Frequency, CGI-I Summary Scores and CGI-I Improver Frequency by Treatment and Visit (Intent to Treat Population)

Appendix 16.1.9.2.5 Statistical Analysis Details of Table 14.2.3.3 and Table 14.2.3.4 Analysis of Clinical Global Impression Severity (CGI-S) Score Change from Baseline (Intent to Treat Population)

Appendix 16.1.9.2.6 Statistical Analysis Details of Table 14.2.4.2 and Table 14.2.4.3 Analysis of Hamilton Anxiety Scale (HAM-A) Change from Baseline (Intent to Treat Population)

Appendix 16.1.9.2.7 Statistical Analysis Details of Table 14.2.5.3 and Table 14.2.5.4 Analysis of Symptoms of Depression Questionnaire (SDQ) Total Score Change from Baseline (Intent to Treat Population)

Appendix 16.1.9.2.8 Statistical Analysis Details of Table 14.2.7.2 Analysis of Inflammatory Markers Change from Baseline at Visit 6 (Intent to Treat Population)

Appendix 16.1.9.2.9 Multiple Imputation Method for Missing Visits Statistical Analysis Details of Table 14.2.2.3.1 and Table 14.2.2.4.1 Analysis of Montgomery-Asberg Depression Rating Scale (MADRS) Total Score Change from Baseline

Appendix 16.1.9.2.10 Multiple Imputation Method for Missing Visits Statistical Analysis Details of Table 14.2.2.5.1 Analysis of Montgomery-Asberg Depression Rating Scale (MADRS) Total Score Change from Baseline at Week 6/EOT

Appendix 16.1.9.2.11 Multiple Imputation Method for Missing Visits Statistical Analysis Details of Table 14.2.2.6.1 Montgomery-Asberg Depression Rating Scale (MADRS) Responders Comparison of TS-121 Treatment versus Placebo at Visit 6 (Intent to Treat Population)

Appendix 16.1.9.2.12 Multiple Imputation Method for Missing Visits Statistical Analysis Details of Table 14.2.3.2.1 Summary and Analysis of Clinical Global Impression Improvement

# Statistical Analysis Plan

Taisho Pharmaceutical R&D Inc.  
Protocol TS121-US201

Final 2.0  
18 Dec 2018

Statistical Analysis Plan (SAP)

CONFIDENTIAL

(CGI-I) Score Frequency, CGI-I Summary Scores and CGI-I Improver Frequency by Treatment and Visit (Intent to Treat Population)

Appendix 16.1.9.2.13 Multiple Imputation Method for Missing Visits Statistical Analysis Details of Table 14.2.3.3.1 and Table 14.2.3.4.1 Analysis of Clinical Global Impression Severity (CGI-S) Score Change from Baseline (Intent to Treat Population)

Appendix 16.1.9.2.14 Multiple Imputation Method for Missing Visits Statistical Analysis Details of Table 14.2.4.2.1 and Table 14.2.4.3.1 Analysis of Hamilton Anxiety Scale (HAM-A) Change from Baseline (Intent to Treat Population)

Appendix 16.1.9.2.15 Multiple Imputation Method for Missing Visits Statistical Analysis Details of Table 14.2.5.3.1 and Table 14.2.5.4.1 Analysis of Symptoms of Depression Questionnaire (SDQ) Total Score Change from Baseline (Intent to Treat Population)

Appendix 16.1.9.2.16 Multiple Imputation Method for Missing Visits Statistical Analysis Details of Table 14.2.7.2.1 Analysis of Inflammatory Markers Change from Baseline at Visit 6 (Intent to Treat Population)

## **SECTION 16.2.1: Disposition**

\*Listing 16.2.1.1 Study Disposition (All Screened Patients)

## **SECTION 16.2.2: Protocol Deviations**

Listing 16.2.2.1 Protocol Deviations

## **SECTION 16.2.3: Analysis Sets**

Listing 16.2.3.1 Assignment to Analysis Populations (Safety Analysis Population)

## **SECTION 16.2.4: Demographics And Baseline Characteristics**

\*Listing 16.2.4.1 Demographics (Safety Analysis Population)

Listing 16.2.4.2.1 Screening and Baseline 17 Items Hamilton Rating Scale (HAM-D) (All Screened Patients)

Listing 16.2.4.2.2 Baseline Major Depressive Disorder Characteristics (Intent to Treat Population)

Listing 16.2.4.3 Medical and Psychiatric History (Safety Analysis Population)

Listing 16.2.4.4 Concomitant Medications (Safety Analysis Population)

Listing 16.2.4.5 Prior Antidepressant Therapy (Safety Analysis Population)

Listing 16.2.4.6.1 Drug Screening Results (Safety Analysis Population)

Listing 16.2.4.6.2 Serology Screen Results (Safety Analysis Population)

Listing 16.2.4.6.3 Pregnancy Test Results (Safety Analysis Population)

## **SECTION 16.2.5: Exposure/Compliance/Drug Concentration**

Listing 16.2.5.1 Investigational Product Dose Compliance (Safety Analysis Population)

Listing 16.2.5.2 Pharmacokinetic Sample Times and Plasma Concentrations (Pharmacokinetic Analysis Population)

# Statistical Analysis Plan

Taisho Pharmaceutical R&D Inc.  
Protocol TS121-US201

Final 2.0  
18 Dec 2018  
CONFIDENTIAL

Statistical Analysis Plan (SAP)

## **SECTION 16.2.6: Efficacy and Pharmacodynamic Data**

- \*Listing 16.2.6.1.1 Montgomery-Asberg Depression Rating Scale (MADRS) Total Score, Total Score Change from Baseline and Responder Status (Intent to Treat Population)
- Listing 16.2.6.1.2 Montgomery-Asberg Depression Rating Scale (MADRS) Item Responses (Intent to Treat Population)
- Listing 16.2.6.2 Clinical Global Impression Severity (CGI-S) and CGI Improvement (CGI-I) (Intent to Treat Population)
- Listing 16.2.6.3 Hamilton Anxiety Scale (HAM-A) (Intent to Treat Population)
- Listing 16.2.6.4 Symptoms of Depression Questionnaire (SDQ) (Intent to Treat Population)
- Listing 16.2.6.5 Plasma Copeptin Observed and Change from Baseline (Intent to Treat Population)
- Listing 16.2.6.6 Inflammatory Markers, IL-1, IL-6, HS-CRP, and TNF- $\alpha$  (Intent to Treat Population)
- Listing 16.2.6.7.1 Salivary Cortisol (Intent to Treat Population)
- Listing 16.2.6.7.2 Hair Cortisol (Intent to Treat Population)
- Listing 16.2.6.7.3 Urinary Cortisol (Intent to Treat Population)
- Listing 16.2.6.8 Patient Characteristics, Demographic and Baseline Pharmacodynamic Biomarkers, Listed with Montgomery-Asberg Depression Rating Scale (MADRS) Total Score Baseline and Change from Baseline (Intent to Treat Population)

## **SECTION 16.2.7: Adverse Events**

- \*Listing 16.2.7.1 Adverse Events (Safety Analysis Population)
- \*Listing 16.2.7.2 Serious Adverse Events (SAEs) (Safety Analysis Population)
- Listing 16.2.7.3 Adverse Events Associated with Study Drug Discontinued (Safety Analysis Population)
- \*Listing 16.2.7.4 Events of Clinical Significance (Safety Analysis Population)
- Listing 16.2.7.5 Overdose Events (Safety Analysis Population)

## **SECTION 16.2.8: Listing of Individual Laboratory Measurements by Subject Number**

- Listing 16.2.8.1.1 Clinical Laboratory Results (Conventional Units): Biochemistry (Safety Analysis Population)
- Listing 16.2.8.1.2 Clinical Laboratory Results (Standard International Units): Biochemistry (Safety Analysis Population)
- Listing 16.2.8.2.1 Clinical Laboratory Results (Conventional Units): Hematology (Safety Analysis Population)
- Listing 16.2.8.2.2 Clinical Laboratory Results (Standard International Units): Hematology (Safety Analysis Population)
- Listing 16.2.8.2.3 Local Clinical Laboratory Results and Corresponding Central Laboratory Results (Conventional Units): Hematology (Safety Analysis Population)
- Listing 16.2.8.3 Clinical Laboratory Results: Urinalysis (Safety Analysis Population)

# Statistical Analysis Plan

Taisho Pharmaceutical R&D Inc.  
Protocol TS121-US201

Final 2.0  
18 Dec 2018  
CONFIDENTIAL

Statistical Analysis Plan (SAP)

- Listing 16.2.8.4 Clinical Laboratory Reference Ranges
- Listing 16.2.8.5.1 Abnormal Clinical Laboratory Values (in Conventional Units) (Safety Analysis Population)
- Listing 16.2.8.5.2 Abnormal Clinical Laboratory Values (Standard International Units) (Safety Analysis Population)

## **SECTION 16.2.9: Vital Signs, Physical Findings And Other Observations Related To Safety**

- Listing 16.2.9.1.1 Vital Signs - Observed Values (Safety Analysis Population)
- Listing 16.2.9.1.2 Vital Signs – Change from Baseline (Safety Analysis Population)
- Listing 16.2.9.2.1 12-Lead Electrocardiogram – Observed Values and Investigator Interpretation (Safety Analysis Population)
- Listing 16.2.9.2.2 12-Lead Electrocardiogram – Change from Baseline Values (Safety Analysis Population)
- Listing 16.2.9.3 Height, Observed and Change from Baseline Weight and BMI (Safety Analysis Population)
- Listing 16.2.9.4 Ophthalmological LOCS III Grading Scores and Best Corrected Visual Acuity Scores Observed and Change from Baseline (Safety Analysis Population)
- Listing 16.2.9.5.1 Columbia-Suicide Severity Rating Scale, Suicidal Ideation (Safety Analysis Population)
- Listing 16.2.9.5.2 Columbia-Suicide Severity Rating Scale, Ideation Intensity and Behavior Detail (Safety Analysis Population)

## APPENDIX A: CLINICALLY SIGNIFICANT LABORATORY OUTLIER CRITERIA

Outlier Criteria [a]		
Analyte	SI Units	Conventional Units
HEMATOLOGY		
Hemoglobin (increase)	Value >2 mmol/L above the ULN	Value >2 g/dL above the ULN
Hemoglobin (decrease)	Value <6.2 mmol/L	Value <10 g/dL
Leukocytes (decrease)	Value <3.0 x10  /L	Value <3.0 x10  /μL
Lymphocytes (increase)	Value >4.0 x10  /L	Value >4.0 x10  /μL
Lymphocytes (decrease)	Value <0.8 x10  /L	Value <0.8 x10  /μL
Neutrophils (decrease)	Value <1.5 x10  /L	Value <1.5 x10  /μL
Platelets (decrease)	Value <75 x10  /L	Value <75 x10  /μL
BIOCHEMISTRY		
Albumin (decrease)	Value <30 g/L	Value <3 g/dL
Alkaline phosphatase (increase)	Value >2.5 xULN	Value >2.5 xULN
ALT (increase)	Value >2.5 xULN	Value >2.5 xULN
AST (increase)	Value >2.5 xULN	Value >2.5 xULN
Bicarbonate (decrease)	Value <16 mmol/L	Value <16 mEq/L
Bilirubin (increase)	Value >1.5 xULN	Value >1.5 xULN
Calcium (decrease)	Value <2.0 mmol/L	Value <8.0 mg/dL
Calcium (increase)	Value >2.9 mmol/L	Value >11.5 mg/dL
Cholesterol (increase)	Value >7.75 mmol/L	Value >300 mg/dL
CPK (increase)	Value >2.5 xULN	Value >2.5 xULN
Creatinine (increase)	Value >1.5 xULN	Value >1.5 xULN
GGT (increase)	Value >2.5 xULN	Value >2.5 xULN
Glucose (decrease)	Value <3.0 mmol/L	Value <55 mg/dL
Glucose (increase)	Value >8.9 mmol/L	Value >160 mg/dL
Magnesium (decrease)	Value <0.5 mmol/L	Value <1.2 mg/dL
Magnesium (increase)	Value >1.23 mmol/L	Value >3.0 mg/dL
Phosphate (decrease)	Value <0.8 mmol/L	Value <2.5 mg/dL
Potassium (decrease)	Value < 3.0 mmol/L	Value < 3.0 mEq/L
Potassium (increase)	Value >5.5 mmol/L	Value >5.5 Meq/L
Sodium (decrease)	Value <130 mmol/L	Value <130 mEq/L
Sodium (increase)	Value >150 mmol/L	Value >150 mEq/L
Triglycerides (increase)	Value >2.5 xULN	Value >2.5 xULN
Uric acid (increase)	Value >0.59 mmol/L	Value >10 mg/dL
URINALYSIS		
Hemoglobin, urine (increase)	Present	Present
Protein, urine (increase)	Result of 2+ or 3+	Result of 2+ or 3+

Notes: LLN = lower limit of normal range; ULN = upper limit of normal range; ALT = alanine aminotransferase; AST = aspartate aminotransferase; CPK = creatine phosphokinase; GGT = gamma-glutamyl transpeptidase.

[a] Outlier values based on Grade 2 (moderate) or higher from the Common Toxicity Criteria for Adverse Events v3.0 (CTCAE) Publish Date: August 9, 2006.

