## ***6.3.16.2 Clinical Safety Laboratory Tests (Biochemistry, Hematology and Urinalysis)***

Clinical laboratory biochemistry and hematology results will be presented, using conventional units (original units, received from the laboratory are consistent with CDISC standards) and standard international (SI) units, will be listed by subject number and study time point [Listing 16.2.8.1.1 through Listing 16.2.8.2.2]. Laboratory analyses will utilize scheduled Visit 3 assessments as baseline values. Only if scheduled Visit 3 result is missing will the latest predose assessment be used as the baseline for that patient and test. Change from baseline will be calculated only for laboratory tests with at least one recorded pre-dose assessment.

Certain hematology test samples were assessed by certain sites’ local laboratory and these will be listed together with the corresponding central laboratory results.

Clinical urinalysis and urinalysis microscopic tests will be listed using conventional units [Listing 16.2.8.3].

Laboratory reference ranges, in conventional and SI units will be listed [Listing 16.2.8.4].

All values outside the clinical reference ranges will be flagged in the data listings. The quantitative abnormal values will be flagged with ‘L’ for values below the lower limit of the clinical reference range and ‘H’ for values above the upper limit of the clinical reference range and included in the listings. In addition, certain qualitative tests may be flagged abnormal ‘A’. The Investigator will assess whether the values outside the clinical reference range are clinically significant and laboratory values outside the reference ranges will be reported as abnormal not clinically significant (NCS) or abnormal clinically significant (CS). Clinically significant laboratory values will be recorded by the Investigator as AEs.

Abnormal laboratory values ordered by test category (biochemistry, hematology and urinalysis), randomized treatment, subject number, laboratory test, date and time will be listed using conventional and SI units [Listing 16.2.8.5.1 and Listing 16.2.8.5.2]. Abnormal CS

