# Statistical Analysis Plan

Taisho Pharmaceutical R&D Inc.  
Protocol TS121-US201

Statistical Analysis Plan (SAP)

Final 2.0  
18 Dec 2018  
CONFIDENTIAL

laboratory values ordered by test category (biochemistry, hematology and urinalysis), randomized treatment, subject number, laboratory test, date and time will be listed using conventional and SI units [Table 14.3.4.1 and Table 14.3.4.2].

Descriptive statistics (n, mean, SD, SE, CV%, minimum, median and maximum) for non-categorical data including biochemistry, hematology and any quantitative urinalysis will be presented by treatment group and time point for both observed values and changes from baseline in conventional units [Table 14.3.5.1.1] and in SI units [Table 14.3.5.1.2]. Urinalysis categorical results (normal or abnormal) will also be tabulated [Table 14.3.5.2].

Biochemistry, hematology and urinalysis shift tables will be constructed that show the change in quantitative laboratory values (or urinalysis normal/abnormal) from baseline to end of treatment [Table 14.3.5.3.1 through Table 14.3.5.3.3].

Critical ranges for clinically significant laboratory outlier criteria (attached Appendix A) and clinically noteworthy changes (Appendix B) will be used to identify values and trends of potential medical importance. A summary of the number and percentage of patients with clinically significant laboratory outliers, based on Appendix A, for each specified laboratory test will be presented [Table 14.3.5.4.1]. The summary will present across scheduled and unscheduled tests after first dose in Visit 3 and across scheduled and unscheduled test during placebo lead-in period. Clinical laboratory outlier values of individual patients will be presented in a listing [Table 14.3.5.4.2]. Similar analyses will be performed for clinically noteworthy changes from baseline [Table 14.3.5.5.1 and Table 14.3.5.5.2].

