# Statistical Analysis Plan

Taisho Pharmaceutical R&D Inc.  
Protocol TS121-US201

Final 2.0  
18 Dec 2018

Statistical Analysis Plan (SAP)

CONFIDENTIAL

Table 14.3.5.2	Summary of Urinalysis Categorical Results (Safety Analysis Population)
Table 14.3.5.3.1	Shift from Baseline to End of Treatment in Biochemistry Laboratory Results (Safety Analysis Population)
Table 14.3.5.3.2	Shift from Baseline to End of Treatment in Hematology Laboratory Results (Safety Analysis Population)
Table 14.3.5.3.3	Shift from Baseline to End of Treatment in Urinalysis Laboratory Results (Safety Analysis Population)
Table 14.3.5.4.1	Number and Percentage of Patients With Clinical Laboratory Outlier Values (Safety Analysis Population) (Safety Analysis Population)
Table 14.3.5.4.2	Individual Patients with Clinical Laboratory Outlier Values (in Conventional Units) (Safety Analysis Population)
Table 14.3.5.5.1	Number and Percentage of Patients With Clinically Noteworthy Laboratory Changes (Safety Analysis Population)
Table 14.3.5.5.2	Individual Patients with Clinically Noteworthy Laboratory Changes (in Conventional Units) (Safety Analysis Population)

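### The two unit columns of the hemoglobin-increase outlier limit in SAP Appendix A describe different levels, and the SAP does not say which column drives the outlier count

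*SAP*

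**What the plan says.** Protocol 10.5.1.2 leaves the criteria for laboratory outliers to the SAP. Appendix A of the SAP supplies them, giving each limit in an SI column and a conventional column. For a hemoglobin increase the entries are "Value >2 mmol/L above the ULN" (SI) and "Value >2 g/dL above the ULN" (conventional). The next row, for a hemoglobin decrease, gives "Value <6.2 mmol/L" in SI units and a value below 10 g/dL in conventional units. Footnote [a] says that the limits are based on grade 2 or higher of a published toxicity scale.

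SAP section 6.3.16.2 puts the appendix to use: "A summary of the number and percentage of patients with clinically significant laboratory outliers, based on Appendix A", is planned as Table 14.3.5.4.1, with the individual patients in Table 14.3.5.4.2. The SAP's list of tables titles the second "Individual Patients with Clinical Laboratory Outlier Values (in Conventional Units"). It gives no unit for the first. The same section presents biochemistry and hematology in conventional and in SI units, and describes the conventional units as those in which the laboratory supplies the results. No section says which column of Appendix A decides whether a patient is an outlier.

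**The concern.** The two columns of a row should be the same limit written in two units. Repeating a number is correct where the units are equivalent (cell counts, or mmol/L against mEq/L for bicarbonate, sodium and potassium) or where the limit is a multiple of the ULN. Hemoglobin in mmol/L and in g/dL is neither, yet the increase row shows the number 2 in both columns.

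At stake is one line of a descriptive safety table. If the count is programmed from the SI column and the patient-level table from the conventional column, a patient can appear in the second and be missing from the first. Appendix B does not cover the gap, because its hemoglobin criterion addresses decreases only.

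**Working it through.** **Inputs, all from SAP Appendix A**

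| Row | SI | Conventional |
|---|---|---|
| Hemoglobin (increase) | > ULN + 2 mmol/L | > ULN + 2 g/dL |
| Hemoglobin (decrease) | < 6.2 mmol/L | < 10 g/dL |

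**Step 1: the table's own conversion factor.** From the decrease row, 6.2 / 10 = 0.62 mmol/L per g/dL. If 6.2 is a rounded figure (6.15 to 6.25), the factor lies between 0.615 and 0.625.

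**Step 2: convert the conventional limit to SI.** 2 g/dL × 0.62 = 1.24 mmol/L (2 × 0.615 = 1.23 to 2 × 0.625 = 1.25). The plan's figure of 2 mmol/L is not reproduced.

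**Step 3: convert the SI limit to conventional units.** 2 mmol/L / 0.62 = 3.23 g/dL (2 / 0.625 = 3.20 to 2 / 0.615 = 3.25).

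**Step 4: size of the gap.** 2.00 / 1.24 = 1.61, so the SI limit is about 61% higher (60% to 63% over the range of the factor). Rounding of 6.2 cannot account for that.

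**Step 5: who is classified differently.** The SI limit is the higher of the two, so the disagreement runs one way. A value above ULN + 2.0 g/dL and up to about ULN + 3.23 g/dL is an outlier in conventional units only. The band is 3.23 − 2.00 = 1.23 g/dL wide (1.20 to 1.25), whatever the ULN.

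Illustration with an assumed ULN of 17.0 g/dL, which is not in the documents:

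| Hemoglobin (g/dL) | Above ULN (g/dL) | Above ULN (mmol/L) | Outlier, conventional | Outlier, SI |
|---|---|---|---|---|
| 19.0 | 2.0 | 1.24 | no | no |
| 19.5 | 2.5 | 1.55 | yes | no |
| 20.2 | 3.2 | 1.98 | yes | no |
| 20.3 | 3.3 | 2.05 | yes | yes |

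Another ULN moves the whole band up or down but does not change its width.

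**Step 6: the other rows, as a side check.** The remaining rows that need a mass-to-molar conversion were converted with standard molar masses, an assumption from outside the documents. The stated SI figures differ from the converted ones by +0.2% and +1.1% (calcium), −0.1% (cholesterol), −1.7% and +0.2% (glucose), +1.3% and −0.3% (magnesium), −0.9% (phosphate) and −0.8% (uric acid). All lie within 2%, against 61% for the hemoglobin increase. The point itself needs only the two hemoglobin rows.

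**The case against.** The conversion is not in dispute. The case on the other side concerns what follows from it.

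First, a reader might infer that the SI cell is the faulty one, with the 2 carried across unconverted. The documents show only that the cells disagree. The toxicity criteria in footnote [a] are not available here, so neither limit can be checked against its source. This stands. That the conventional cell is the intended one is a reasonable inference from the units the laboratory reports and the units of the patient-level table, but it is not shown.

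Second, a reader might infer that the safety summary will undercount hemoglobin rises. The documents do not support that either. Where the SAP wants SI output it creates a separate SI table (14.3.4.2 beside 14.3.4.1, and 14.3.5.1.2 beside 14.3.5.1.1). It plans no SI table for outliers, and Table 14.3.5.5.2, the patient-level table for noteworthy changes, is also in conventional units. Counting in conventional units is therefore the more natural reading, and under it the counts are unaffected. This stands too, but the unit of Table 14.3.5.4.1 is still left unstated.

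Third, an omitted patient would not be lost. Values outside the reference range are flagged, abnormal values are listed in both unit systems (Listings 16.2.8.5.1 and 16.2.8.5.2), and the investigator judges their clinical significance. The band is also likely to hold few patients or none: protocol 7.1.2 excludes clinically significant hematology abnormalities at Visit 1, and protocol 4.4.3 does not name raised hemoglobin among the potential risks. These arguments limit the consequence but do not make the two cells agree.

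Finally, it would be too much to say that every other pair agrees to rounding. With the standard molar mass, 55 mg/dL of glucose is 3.05 mmol/L against the stated 3.0. That difference is under 2% and does not bear on the hemoglobin row.

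**Conclusion.** The inconsistency is real and can be shown from Appendix A alone: two adjacent hemoglobin rows imply different conversions, and the increase limit differs between columns by about 61%, or 1.23 g/dL. It is a minor point. It changes a reported count only if Table 14.3.5.4.1 is programmed from the SI column and a patient falls in the band. Neither condition can be settled from the documents, and the first is the less natural reading. No test or decision rule is attached to the table, and the efficacy analysis is untouched.

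The conclusion rests on the decrease row being a correct conversion. The assumed ULN serves only the illustration, and the outside molar masses only the side check.

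**What to change.** Reconcile the two hemoglobin-increase cells in Appendix A. The likely change is to the SI entry, to about >1.24 mmol/L above the ULN, after the sponsor has confirmed the 2 g/dL figure against the toxicity criteria in footnote [a]. If those criteria support a different limit, both columns should be derived from it.

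Add one sentence to SAP section 6.3.16.2 stating that Table 14.3.5.4.1 is derived from conventional-unit values, as Table 14.3.5.4.2 is. That removes the ambiguity for every row of the appendix, including the small glucose difference.

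The cost is one number, one sentence and one check against a source that the sponsor already cites. No data collection or other analysis changes.
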